11.6.2 Ophthalmologic Examination

Ophthalmologic examinations of both eyes will be performed at the visits specified in Table 1; the time points during each visit are specified in Table 2, Table 3, Table 4, and Table 5 for Cohorts A, B, C, and D, respectively. Both eyes will be assessed at each examination unless otherwise specified. Ophthalmologic examination results will be summarized for the study eye, the non-study eye, and either eye. Summaries for either eye will be presented for MDTP only.

11.6.2.1 Manifest Refraction

Manifest refraction will be determined at the following visits in order to assess BCVA:

- Screening
- SDTP (Cohort A only): baseline (Day -2)
- MDTP (all cohorts): baseline (Day -2) and Day 29.

The manifest refraction will be repeated if the BCVA has decreased by 10 or more letters.

The status of manifest refraction assessment, and the date and time of the assessment will be listed by individual subject. No summarization of refraction data will be performed.

11.6.2.2 Best-Corrected Visual Acuity

Using the manifest refraction, the BCVA will be assessed at distance before slit lamp examination at the following visits:

- Screening
- Midwashout assessment
- SDTP (Cohort A only): baseline (Days -2 and -1) and Days 1 and 2
- MDTP (all cohorts): baseline (Days -2 and -1) and Days 1, 2, 7, 14, 21, 27, 28, and 29.

See [Table 2](#), [Table 3](#), [Table 4](#), and [Table 5](#) for detailed timings by cohort.

For each treatment period, the baseline assessments are measured on Day -2 and -1 at predose/morning, +1 and +12 hours. Baseline BCVA is defined as the mean of the non-missing assessments at these 6 time points. A decrease in BCVA by 6 or more letters may be considered clinically significant (CS) or not clinically significant (NCS) and requires a dilated posterior segment examination. A 10 or more letter loss in BCVA is considered CS and requires a repeat manifest refraction and dilated posterior segment examination. Clinically significant changes should be recorded as AEs in the source document and eCRF.

Descriptive statistics for BCVA letter score and changes from baseline at each assessment time point will be presented by eye (study eye, non-study eye, and either eye (MDTP only)) and treatment. Additionally, the number and percentage of subjects with BCVA changes in following categories by treatment group will be presented:

- < 6 letter decrease
- 6 to 9 letter decrease
- ≥ 10 letter decrease

The percentages will be calculated relative to the number of subjects with available baseline BCVA and at the postbaseline assessment for the given timepoint. The complete results of BCVA will be listed by individual subject.

For either eye summaries, at baseline the eye with the lower baseline BCVA score will be summarized. For post baseline timepoints, the eye with the smaller increase from baseline will be summarized. If both eyes have the same change from baseline, the eye with the lower BCVA score at the given visit will be summarized.

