11. SAFETY ANALYSES

The safety analysis will be performed using the Safety set. Safety and tolerability will be assessed by monitoring AEs, vital sign measurements, clinical laboratory test values, ECG readings, antidrug antibodies, drop comfort assessment, and ophthalmologic examinations. SDTP and MDTP outputs will be summarized separately. For SDTP, data will be summarized for two periods:

- a. Dosing period only: Day 1 SDTP – Day 2 SDTP
- b. Dosing period and washout period: Day 1 SDTP up to First Dose MDTP

For SDTP, ocular summaries will be presented for the study eye and the non-study eye. For MDTP, all ocular summaries will be presented for the study eye, the non-study eye, and for either eye. For summarization by either eye, the eye with the less favorable response at the given timepoint will be summarized which may result in different eyes being summarized at different visits. Adverse events and selected ocular assessments summaries will also be presented for both eyes. For summarization by both eyes, subjects with events or assessments occurring in both eyes will be included. In the MDTP, ocular summaries will be presented first by dose regimen then by dose level and placebo subjects will be pooled by dosing regimen. (eg, QD placebo subjects will be pooled together, BID placebo subjects will be pooled together, TID placebo subjects will be pooled together, and QID placebo subjects will be pooled together.) All subjects in the Safety set (including placebo-treated subjects) within a regimen will also be presented. (For example, all active QD doses and QD placebo patients will be combined for the QD dosing regimen summaries.)

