11.6.2.4 Conjunctival Redness Score Assessment

The Efron scale/conjunctival redness assessment ([Efron et al. 2001](#)) is a clinically validated, image-based scale that will be used to evaluate bulbar conjunctival redness during all ophthalmologic examinations, as outlined in [Table 1](#) (all cohorts) and specified in [Table 2](#), [Table 3](#), [Table 4](#), and [Table 5](#) for Cohorts A, B, C, and D, respectively. The scale contains 5 categories ranging from 0 (normal) to 4 (severe).

For each treatment period, the baseline assessments are measured on Day -2 and -1 at predose/morning, +1, +3, +6, and +12 hours. Baseline conjunctival redness score is defined as

the single assessment at Day -1. A separate baseline will be derived for each scheduled time point. Change from baseline will be calculated comparing post treatment values to their respective baseline (e.g., on treatment predose assessments will be compared to baseline predose assessments, on treatment 1 hours assessments will be compared to baseline 1 hour assessments, on treatment 3 hours assessments will be compared to baseline 3 hour assessments, on treatment 6 hours assessments will be compared to baseline 6 hour assessments and on treatment 12 hours assessments will be compared to baseline 12 hour assessments).

The number and percentage of subjects in each score category at each time point will be summarized by eye (study eye, non-study eye, and either eye (MDTP only)), and treatment. For either eye assessments, the eye with the greater score will be summarized. The denominator of the percentage is the number of subjects who have the assessment for the specified eye and visit. In addition, the number and percentage of subjects with clinically significant results, and non-clinically significant results will be summarized by treatment group. Results of conjunctival redness score assessment will be listed by individual subject.

Additionally, the number and percentage of subjects with conjunctival redness score changes from baseline in the following categories by eye (study eye, non-study eye, and either eye (MDTP only)) and treatment group will be presented:

- -4 (4 points decreased from baseline)
- -3 (3 points decreased from baseline)
- -2 (2 points decreased from baseline)
- -1 (1 point decreased from baseline)
- 0 (no change from baseline)
- 1 (1 point increased from baseline)
- 2 (2 point increased from baseline)
- 3 (3 point increased from baseline)

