11.6.2.6 Corneal Epithelial Integrity by Fluorescein Stain

The integrity of the corneal epithelium will be assessed using topically applied fluorescein at the time points outlined in [Table 1](#) (all cohorts) and specified in [Table 2](#), [Table 3](#), [Table 4](#), and [Table 5](#) for Cohorts A, B, C, and D, respectively. It is important to perform the assessment before instillation of topical anesthetic for measurement of IOP.

For each subject at each visit and timepoint, a total score of three components from corneal epithelium integrity will be calculated by adding scores across three regions: inferior, central, and superior for each eye. The total scores will be summarized. For each treatment period, the baseline assessments are measured on Day -2 and -1 at predose/morning, +2, +4, +8, and +12 hours. Baseline corneal epithelial integrity is defined as the single assessment at Day -1 at each scheduled time point. Change from baseline will be calculated comparing post treatment values to their respective baseline (e.g., on treatment predose assessments will be compared to baseline predose assessments, on treatment 2 hours assessments will be compared to baseline 2 hour assessments, on treatment 4 hours assessments will be compared to baseline 4 hour assessments, on treatment 8 hours assessments will be compared to baseline 8 hour assessments and on treatment 12 hours assessments will be compared to baseline 12 hour assessments).

Descriptive statistics for corneal epithelial integrity total scores and change from baseline at each assessment time point will be presented by eye (study eye, non-study eye, and either eye (MDTP only)) and treatment group. For either eye summaries, at baseline the eye with the greater staining total score will be summarized. For post baseline timepoints, the eye with the greater increase from baseline will be summarized. If both eyes have the same change from baseline, the eye with the greater staining total score at the given visit will be summarized. In addition, the number and percentage of subjects with clinically significant results, and non-clinically significant results will be summarized by treatment group. Results of corneal epithelium integrity assessment including individual region scores will be listed by individual subject and clinically significant findings will also be presented.

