The number and percentage of subjects who have no notch at baseline and a notch present at any time during post baseline period will be summarized by eye (study eye, non-study eye, and either eye (MDTP only)) and treatment. Only subjects who have no notch at baseline will be included in this summary. Baseline notch presence is defined as the Day -2 baseline assessment. For either eye summaries, a subject will be counted as notch absent if both eyes have no notch and as notch present if either eye has a notch. The percentages will be calculated relative to the number of subjects with available baseline notch assessment and at the postbaseline assessment for the given timepoint.

In addition, the number and percentage of subjects with changes in number of notches from baseline in the following categories by treatment group will be presented:

- 0 (no change)
- 1+ (increase by 1 notch)
- 2+ (increase by 2 notches)

- 3+ (increase by 3 notches)
- 4+ (increase by 4 notches)

The percentage will be calculated relative to the number of subjects with available baseline notch assessment and at the postbaseline assessment for the given timepoint. For either eye summaries, the eye with greatest increase in number of notches will be summarized.

Results of posterior segment examination will be listed by individual subject and a separate listing of clinically significant findings will also be presented.

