11.6.2.12 Noncontact Specular Microscopy

Noncontact specular microscopy will be performed, with the subject seated, to assess endothelial cell count at the following visits:

- Screening
- SDTP (Cohort A only): baseline (Day -1) and Day 2
- MDTP (all cohorts): baseline (Day -1) and Days 14 and 29.

Details of the procedure will be found in the ophthalmology procedures manual.

For each eye and timepoint assessed, three measurements of central endothelial cell density (cells/mm²) will be made. All measurements will be recorded in the source document and eCRF and the mean of the 3 readings for each eye will be used to determine the mean cell density at the given time point for each eye. These mean density values will be used for all specular microscopy analyses of cell density.

Baseline specular microscopy cell density is defined as the mean of the 3 readings on Day -1. Descriptive statistics for the mean central endothelial cell density and changes from baseline at each assessment time point will be presented by eye (study eye, non-study eye, and either eye (MDTP only)) and treatment group. For either eye summaries, the eye with the smaller cell density will be summarized at baseline. For post baseline assessment, the eye with the greater

decrease from baseline will be summarized. If both eyes have the same change from baseline, the eye with the smaller value will be summarized. Results of noncontact specular microscopy will be listed by individual subject.

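### Either-eye rows pick the eye by worse value at baseline but by worse change afterwards, so post-baseline actual values are not comparable with baseline; the either-eye new-notch rule has a related gap

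*SAP*

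**What the plan says.** SAP section 11 sets the general aim: "For summarization by either eye, the eye with the less favorable response at the given timepoint will be summarized". It adds that the eye shown may differ from visit to visit.

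For BCVA (11.6.2.2) the either-eye rule has two halves. The first is that "at baseline the eye with the lower baseline BCVA score will be summarized". The second is "For post baseline timepoints, the eye with the smaller increase from baseline will be summarized". The lower score is used after baseline only to break a tie in change.

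The same pair of rules appears in four more sections. For staining (11.6.2.6) the baseline eye is the one with the greater total, and then "For post baseline timepoints, the eye with the greater increase from baseline will be summarized". For cell density (11.6.2.12), "For either eye summaries, the eye with the smaller cell density will be summarized at baseline", followed by the eye with the greater fall. Cup-to-disc ratio (11.6.2.10) and pachymetry (11.6.2.13) follow the same pattern.

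All five sections summarize both actual values and changes for either eye. The output list prints them together in MDTP tables 14.3.7.2.2, 14.3.7.6.2, 14.3.7.10.4, 14.3.7.12.2 and 14.3.7.13.2, with a percentage-change version for pachymetry in 14.3.7.13.3.

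Redness (11.6.2.4) is handled differently for scores: "For either eye assessments, the eye with the greater score will be summarized", at every time point. Its change categories go to a separate table.

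The new-notch summary (11.6.2.10) admits only subjects without a notch at baseline. For either eye, a subject is "counted as notch absent if both eyes have no notch and as notch present if either eye has a notch".

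**The concern.** Safety is the primary objective, and the either-eye row is meant to give the less favorable view. A reader of one of these tables will compare the post-baseline actual value with the baseline above it. The two come from eyes chosen on different criteria, so their difference is not the change of any eye and need not match the printed change. After baseline, the eye with the worse level is shown only if it also has the worse change or ties. Section 11 discloses that the eye may switch. It does not disclose that the criterion switches after baseline.

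The notch rule works against its purpose in another way. A subject with a notch in one eye at baseline leaves the either-eye table altogether, even if the fellow eye later develops one.

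**Working it through.** The plan states no figure on this point, so there is none to reproduce.

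**1. The rules side by side**

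| SAP section | Baseline eye | Post-baseline eye | Data behind baseline / post-baseline |
|---|---|---|---|
| 11.6.2.2 BCVA | lower score | smaller increase | mean of up to 6 readings / 1 reading |
| 11.6.2.6 staining | greater total | greater increase | 1 / 1 |
| 11.6.2.10 cup-to-disc | greater ratio | greater increase | 1 / 1 |
| 11.6.2.12 cell density | smaller density | greater decrease | mean of 3 / mean of 3 |
| 11.6.2.13 pachymetry | thinner | greater decrease | mean over 5 time points / 1 time point |

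**2. One subject, no assumptions.** Eyes at 70 to 70 and 85 to 84 letters have changes of 0 and -1. The either-eye row prints baseline 70, post-baseline 84, change -1. The actual value rises by 14 while the change is negative, and the 70-letter eye is absent. For any subject the value shown is one of the two eyes' values, so it can never be worse than the worse eye's. Against a worst-value rule the error runs one way only.

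**3. Expected drift with no drug effect.** Model: baseline = true value + mean of k errors; post-baseline = true value + one error. Errors are normal and independent between eyes and visits. Tau is the per-eye between-eye SD of true values and s is the single-reading SD. Neither is in the documents, so both are assumptions. With "worse" meaning lower:

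- Baseline row: mu - sqrt(tau^2 + s^2/k)/sqrt(pi)
- Post-baseline actual row: mu - [s^2/sqrt(s^2 + s^2/k)]/sqrt(pi)
- Change row: -sqrt(s^2 + s^2/k)/sqrt(pi)

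The actual row moves toward improvement when (tau/s)^2 > k/(k+1) - 1/k:

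- BCVA, k = 6: 0.857 - 0.167 = 0.690, so tau > 0.83 s.
- If the six readings are worth only two independent ones: 0.667 - 0.500 = 0.167, so tau > 0.41 s.
- Pachymetry, k = 5: 0.833 - 0.200 = 0.633, so tau > 0.80 s.
- Equal precision at both visits, k = 1: 0.5 - 1 is negative, so always on a continuous scale.

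Simulation (400,000 subjects per scenario), drift in units of s:

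| tau/s | k=6 drift | k=6 worse eye not shown | k=6 drift, worst-value rule | k=1 drift | k=1 worse eye not shown |
|---|---|---|---|---|---|
| 0 | -0.29 | 12% | -0.34 | +0.16 | 25% |
| 1 | +0.09 | 27% | -0.19 | +0.40 | 33% |
| 2 | +0.63 | 36% | -0.11 | +0.86 | 40% |
| 3 | +1.18 | 41% | -0.08 | +1.39 | 43% |

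The change row is about -0.61 s (k = 6) or -0.80 s (k = 1) throughout. For k = 1 the worst-value rule has no drift.

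**4. In units**

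- BCVA, s = 2 letters, readings rounded to whole letters: drift is -0.34, +0.13, +0.66, +1.21 and +2.30 for tau = 1, 2, 3, 4 and 6. The change row shows -1.23 each time.
- Cell density, reading SD 80, so the SD of a mean of 3 is 80/sqrt(3) = 46.2. For an SD of the between-eye difference from 80 to 250, tau = 80/sqrt(2) to 250/sqrt(2) = 57 to 177. Drift is [sqrt(57^2 + 46.2^2) - 46.2/sqrt(2)]/sqrt(pi) = +23, rising to +85 cells/mm2. The change row is -46.2 x sqrt(2)/sqrt(pi) = -37.
- A true 2-letter loss in both eyes (s = 2): the actual row moves -1.86, -1.34, -0.80 and +0.29 for tau = 2, 3, 4 and 6. At tau = 4 a worst-value rule gives -2.22.
- Between arms at tau = 4, loss against no effect: -0.80 - 1.21 = -2.01 under the SAP rule and -2.22 - (-0.21) = -2.01 under a worst-value rule.

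**5. Coarse scale.** With whole-point changes of plus or minus 1, ties are frequent and the tie-break returns the worse value. Drift is then only 0.005 to 0.009 points toward improvement when 5 to 30% of eyes change, and 0.047 toward worsening at 60%.

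**6. Notch.** Right eye notched at baseline, left eye not; the left eye develops a notch. The single-eye table for the left eye counts 1. The either-eye table excludes the subject and counts 0.

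**The case against.** The strongest reply is that little is lost. Each of these sections also tabulates study eye and non-study eye separately, and every result is listed by subject. The change rows and the 6-to-9 and 10-or-more letter categories use the worse change, and clinically significant BCVA changes become AEs. All of that stands and limits the point to one row per table.

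It can also be said that taking value and change from one eye is coherent, and that section 11 may mean change by response. That would justify the change row. It does not make the actual values before and after baseline comparable.

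Two stronger readings are tempting, and the documents support neither.

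- A reader might infer that either-eye values drift toward improvement in every arm whatever the data. The plan gives no SDs. For BCVA the drift reverses when the eyes are similar relative to reading noise, true worsening can outweigh it, and on a graded scale such as staining ties largely remove it.
- A reader might infer that an eye at risk is hidden, for example one falling below 2000 cells/mm2. That figure is an entry criterion, the SAP tabulates nothing against it after baseline, and the eye still appears in its single-eye table and the listing.

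On notches, table 14.3.7.10.8 (change in number of notches) takes the eye with the greatest increase and so would register the fellow eye. It covers the gap only in part: an increase there may be in an eye already notched, and the output list does not mark that table for the interim analysis, whereas the new-notch table 14.3.7.10.6 is marked.

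**Conclusion.** The point holds, as a minor one. In five sections the either-eye post-baseline actual value is not comparable with its baseline, is biased toward improvement relative to a worst-value rule, and can contradict the change printed in the same table. That much follows from the text alone.

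The size rests on assumed SDs. For BCVA with a 2-letter reading SD, the no-effect drift runs from -0.34 to +2.30 letters as the between-eye SD goes from 1 to 6. With no effect, the artefact is similar in expectation in active and placebo, because both eyes are dosed in the MDTP and the same rule applies. It therefore distorts levels within an arm more than the contrast between arms. Separately, the either-eye new-notch count can fall below a single-eye count.

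**What to change.** In 11.6.2.2, 11.6.2.6, 11.6.2.10 (cup-to-disc), 11.6.2.12 and 11.6.2.13, select separately for either-eye summaries:

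- actual value: the worse value of the two eyes at that visit and time;
- change: the worse change of the two eyes;
- footnote: the two may come from different eyes.

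In 11.6.2.10, define an either-eye new notch as at least one eye that was notch-free at baseline having a notch afterwards, among subjects with at least one notch-free eye at baseline and a post-baseline assessment.

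The cost is SAP wording and one derived variable per measure, with no new data. There are two downsides. Value and change in a table may no longer belong to the same eye. For BCVA a no-effect shift toward worsening remains (0.08 to 0.34 s across the scenarios above; 0.21 letters at s = 2, tau = 4), because baseline averages six readings and later values do not.

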11.6.2.3 Slit Lamp Biomicroscopy

Slit lamp biomicroscopy will be performed at the following visits:

- Screening
- Midwashout assessment
- SDTP (Cohort A only): baseline (Days -2 and -1) and Days 1 and 2
- MDTP (all cohorts): baseline (Days -2 and -1) and Days 1, 2, 7, 14, 21, 27, 28, and 29.

See [Table 2](#), [Table 3](#), [Table 4](#), and [Table 5](#) for detailed timings by cohort.

Slit lamp assessments will be performed before IOP measurement and pachymetry. Ungraded slit lamp assessments will be made before graded assessments.

The following anterior structures will be evaluated as normal or abnormal. If abnormal, the findings should be described and recorded as either CS or NCS for the overall slit lamp biomicroscopy examination. Any CS findings should be recorded as AEs; the investigator may use his/her discretion to determine whether a finding considered NCS is reported as an AE. Findings and assessment of clinical significance should be recorded in the source documents and eCRF.

The following will be examined at each visit:

- Lids/lashes/lacrimal
- Conjunctiva
- Cornea
- Anterior chamber
- Iris
- Lens (at Screening and Day 29 during dilated exams only)

The findings of overall slit lamp biomicroscopy examination will be summarized for the study eye, the non-study eye, and if observed in either eye (MDTP only) at each visit by treatment. The number and percentage of subjects with clinically significant abnormal results, and non-clinically significant abnormal results for overall slit lamp biomicroscopy examination will be also summarized at each visit by treatment. For either eye summaries, a subject will be counted as normal only if both eyes are normal and as abnormal if either eye is abnormal. The percentage of subjects with each findings by ocular location will be calculated relative to the number of subjects with available finding at specific eye and visit. Additionally the number and percentage of subjects with at least one postbaseline abnormal finding for each ocular location will be summarized. Results of slit lamp biomicroscopy will be listed by individual subject and a separate listing of clinically significant findings will also be presented.

